**11.4.4 OTHER IMPORTANT CLINICAL EFFECTIVENESS OUTCOMES**

The analysis will be based on the PP Population.

For subjects treated with hypotensive medications at Screening Visit, the change in number of hypotensive medications from Screening to 12 Month (before washout if it is needed) will be calculated. For subjects treated with SSIs the change in number of hypotensive medications will be assumed to be 0. The descriptive statistics such as mean, standard deviation, median, minimum, and maximum will be used to summarize the change in number of hypotensive medications used at 12 months from Screening. The 95% confidence interval of the mean change will be calculated based on the t-distribution.

The percent change in unmedicated DIOP from baseline to 12 months will be calculated for each eye in the PP population. For eye treated with SSI, the baseline unmedicated DIOP will be used to impute the 12 month unmedicated IOP (i.e. 0% change). The descriptive statistics such as mean, standard deviation, median, minimum, and maximum will be used to summarize the percent change in unmedicated DIOP at 12 months. The 95% confidence interval of the mean percent change will be calculated based on the t-distribution.

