#### Secondary IOP-Lowering Interventions to Control IOP

If the subject requires another glaucoma procedure to control their IOP, the subject should continue to be followed according to standard of care until the adverse event resolves or 1 month post-re-intervention, whichever is longer. Following this, the subject should be withdrawn from the study.

Subjects who have a secondary IOP-lowering intervention will be considered treatment failures for the purpose of the endpoint analyses. These subjects will be included in the Safety Endpoint analyses through their withdrawal from the study.

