## **11.2 ANALYSIS POPULATIONS**

The intent-to-treat (ITT) analysis population includes all subjects who are enrolled and treated, regardless of whether or not they have a protocol deviation. The per-protocol analysis population (PP) is a subset of ITT, which includes all subjects who have ab-interno transluminal viscoelastic delivery and trabeculotomy, 12 month IOP (or hypotensive medications washed out IOP if the medications can be washed out) and medication data, and have no clinically significant protocol deviations. It should be noted that the ITT subjects with an uneventful study procedure but with SSIs before the 12-month visit will be included in the PP population even if they do not have the 12-month IOP and medication data. The primary analyses on the primary and secondary endpoint analyses will be carried out on the per-protocol population.

The safety data will be summarized based on the ITT population. The primary and secondary endpoint analyses will also be performed on the ITT population.

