### **11.4.1 PRIMARY EFFECTIVENESS ENDPOINT**

Proportion of eyes with a  $\geq 20\%$  decrease in unmedicated mean diurnal IOP at the 12-month postoperative examination compared to baseline will be calculated. The binomial distribution will be used to derive the exact 95% confidence interval of the percent. The

proportion will be compared against the performance goal of 0.4 (or 40%) based on binomial distribution.

[REDACTED]

For the analyses based on the ITT population, the following imputation for subjects with missing 12-month data but without SSI may be performed:

- The within-eye worst IOP (collected after 3 months postoperatively or IOP at baseline for the subjects with no data after postoperative 3 months) for the missing 12-month IOP and worst number of IOP lowering medications (collected after 3 months postoperatively or IOP-lowering medication data at baseline for the subjects with no data after postoperative 3 months) for the missing 12-month number of IOP-lowering medications.
- The worst IOP (collected after 3 months postoperatively or IOP at baseline for the subjects with no data after postoperative 3 months) during the study for the missing 12-month IOP and worst number of IOP-lowering medications (collected after 3 months postoperatively or IOP-lowering medication data at baseline for the subjects with no data after postoperative 3 months) during the study for the missing 12-month number of IOP-lowering medications.
- The mean IOP during the study for the missing 12-month IOP and mean number of IOP-lowering medications during the study for the missing 12-month number of IOP-lowering medications.
- The last-observed-carried-forward approach.

**11.4.2** [REDACTED]

[REDACTED]

[REDACTED]

[REDACTED]

- [REDACTED]

[REDACTED]

[REDACTED]

[REDACTED]

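### Section 11.4.4 sets the medication change to 0 for every eye with a secondary intervention, even where the record shows more medications than at Screening

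*Combined protocol and SAP*

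**What the plan says.** Section 11.4.4 defines the outcome as follows: "For subjects treated with hypotensive medications at Screening Visit, the change in number of hypotensive medications from Screening to 12 Month", counted before any washout. The population is stated at the top of the section: "The analysis will be based on the PP Population". The rule for eyes with an SSI is "For subjects treated with SSIs the change in number of hypotensive medications will be assumed to be 0". The summary consists of mean, standard deviation, median, minimum and maximum, and "The 95% confidence interval of the mean change will be calculated based on the t-distribution". The section contains no hypothesis test.

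Three other places bear on the rule:

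- Section 9.9, under the heading on secondary IOP-lowering interventions: "Subjects who have a secondary IOP-lowering intervention will be considered treatment failures for the purpose of the endpoint analyses".
- Section 9.9 also requires hypotensive medications that are added, stopped or changed to be entered on a case report form, at scheduled visits and, if necessary, at unscheduled ones.
- Section 11.2 generally requires Month 12 data for the per-protocol population. It makes an exception for subjects with an uneventful study procedure and an SSI before Month 12, who "will be included in the PP population even if they do not have the 12-month IOP and medication data".

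**The concern.** The three places together mean that SSI eyes do enter this summary, that their medication history up to the SSI is on file, and that the plan regards them as failures. The value entered is nevertheless fixed at no change, whatever the history shows.

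If an eye needed more medications than at Screening before it was re-operated, 0 is not a failure value on this outcome. It is better than what was observed. The protocol foresees escalation of this kind: a footnote to section 10.2 has separate reporting terms for an IOP rise managed with systemic medication and for secondary surgery to manage IOP.

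What is at stake is a reported estimate. Use of IOP-lowering medications is one of the two effects named in the study objective (section 2), and the mean change with its interval is a natural figure to quote from the study.

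**Working it through.** **Inputs from the documents.** The SSI value is 0 (11.4.4). The subjects are those on medication at Screening, in the per-protocol population (11.4.4). Section 11.1 gives 91 evaluable eyes for the primary endpoint. The documents give no SSI rate, no medication count before an SSI, and no number of subjects medicated at Screening.

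**The figure of 91.** The plan has no figure for the medication outcome, so 91 serves only as a working denominator. It can be reproduced. With a null rate of 0.40, a true rate of 0.55, one-sided 0.025 and 80% power, the one-sample normal formula is

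n = [(1.960 × √(0.40 × 0.60) + 0.842 × √(0.55 × 0.45)) / 0.15]² = 84.5.

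The continuity correction gives

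(84.5 / 4) × (1 + √(1 + 2 / (84.5 × 0.15)))² = 91.05, in line with the stated 91.

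**One eye.** Take change as the later count minus the Screening count, so that a positive value means more medications. An eye with 2 medications at Screening and 3 at the last visit before the SSI has a recorded change of +1; section 11.4.4 enters 0. An eye with 3 at Screening and 1 before the SSI has a recorded change of −2; section 11.4.4 again enters 0, which here counts against the device.

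**The mean.** Let N be the number of analysed eyes, s the number with an SSI, and d the mean recorded change in those s eyes.

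Mean using the record − mean under the 0 rule = (s / N) × d.

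A positive result means that the 0 rule makes the mean too favourable. With N = 91 and assumed values of s and d:

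| SSI eyes (share) | d = +1 | d = +2 | d = −1 |
|---|---|---|---|
| 1 (1.1%) | 0.011 | 0.022 | −0.011 |
| 3 (3.3%) | 0.033 | 0.066 | −0.033 |
| 5 (5.5%) | 0.055 | 0.110 | −0.055 |
| 9 (9.9%) | 0.099 | 0.198 | −0.099 |

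**Smaller denominator.** Section 11.4.3 lists 0 medications at Screening as a possible category, and eyes in it are outside this summary, so N may be smaller. At an assumed N = 60, the shift for d = +1 is 1/60 = 0.017 to 9/60 = 0.15.

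**Mixed histories.** Suppose that, of 5 SSI eyes, 2 are at +1 and 3 at −1. The recorded changes sum to −1, so the record moves the mean by −1/91 = −0.011: on balance the 0 rule is slightly unfavourable to the device. The two increases are still hidden. Taking the larger of 0 and the recorded change would move the mean by +2/91 = +0.022.

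**Maximum and interval.** The reported maximum cannot show an increase in an SSI eye. The centre of the confidence interval moves with the mean. If the mean change is a reduction, replacing a positive value by 0 also brings it closer to the mean and so narrows the interval.

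**The case against.** The case for leaving the rule alone has several parts.

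- **No Month 12 value is being discarded.** Section 9.9 has SSI subjects withdrawn after a period of follow-up, so most will have no Month 12 count. A count before the SSI belongs to another time point. That stands: it is evidence about the eye, not the outcome itself.
- **Zero is a prespecified no-benefit value.** It matches the neighbouring rule that gives SSI eyes a 0% change in unmedicated diurnal IOP. That also stands, and for an eye at or below its Screening count 0 is neutral or harsh. It does not answer the case of an eye whose recorded count was above Screening.
- **An increase over Screening may be uncommon.** Section 9.9 recommends no IOP-lowering medication after surgery unless warranted, so a subject medicated at Screening must first climb back to the Screening count. Drops added after surgery are not the same as drops above Screening. The documents do not settle how often it happens.

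A reader might go further and infer that a documented failure is scored better than an ordinary dropout, because section 11.4.1 mentions the "worst number of IOP lowering medications (collected after 3 months postoperatively" as an imputed value. The documents do not support that. Section 11.4.4 uses the per-protocol population, which requires "12 month IOP (or hypotensive medications washed out IOP if the medications can be washed out) and medication data" from subjects without an SSI, so ordinary dropouts receive no score in this summary. The 11.4.1 imputations are optional, apply only to ITT analyses of subjects without an SSI, and include two options (study mean and last observation carried forward) that need not be worst-case. The worst-value options also fall back on baseline medication data when nothing was recorded after 3 months. Baseline follows washout (section 9.5), so read literally that count could be 0.

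**Conclusion.** The point holds in a limited form. The 0 rule is unconditional, the overriding data are collected, and for an SSI eye with a recorded increase over Screening the entered value is better than the record.

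Under the assumption of 91 analysed eyes with 1 to 9 SSI eyes, each one medication above Screening, the mean is too favourable by about 0.01 to 0.10 medications, and by up to about 0.20 at two medications. It is 0 if no SSI eye had an increase. The SSI numbers and the counts are assumptions; a smaller medicated group would enlarge the shift in proportion.

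It would be tempting to say that the rule biases the mean toward benefit in general. It does not: SSI eyes on fewer medications than at Screening are scored against the device, and the net effect can have either sign.

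The outcome is descriptive. No test in 11.4.4 and no primary endpoint result depends on the rule. Sections 11.4.2 and 11.4.5 are redacted, so whether the same handling is used or supplemented there cannot be checked. This is a minor improvement to the plan.

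**What to change.** In section 11.4.4, replace the SSI sentence with a rule of this kind: for a subject with an SSI, the change in number of hypotensive medications is the larger of 0 and the recorded change from Screening at the last visit, scheduled or unscheduled, before the SSI. If no count was recorded between surgery and the SSI, the value is 0.

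If the 0 rule is to be kept for its parallel with the IOP rule, the minimum is to report this version beside it as a prespecified sensitivity analysis, with the number of SSI eyes and their last recorded counts.

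The cost is one sentence and a small programming change, with no new data. The mean may be slightly less favourable. The rule is deliberately one-sided, since it keeps recorded increases and ignores recorded decreases, and the report should say so. A last count may also include short-term treatment, for example for a steroid response, which a listing of the SSI eyes would show.

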**11.4.5**

[REDACTED]

[REDACTED]

- [REDACTED]
- [REDACTED]
- [REDACTED]
- [REDACTED]
- [REDACTED]

[REDACTED]

## **11.5 SAFETY ANALYSIS**

All safety analyses will be performed on the ITT population based on all available data descriptively.

### **11.5.1 ADVERSE EVENT**

Adverse events (AEs) will be classified as pretreatment, intraoperative or postoperative. The number and the percent of eyes reporting at least 1 adverse event of a given type will be summarized. Additionally, the number of reports of each type of AEs will be provided.

For each AE, the number and the percent of eyes reported with the event will be summarized by the severity level. For eyes with multiple reports of the same type of AE, the maximum severity will be used. Similarly, the AE relationship to the procedure will be summarized. For eyes with multiple reports of the same type of AE, the closest relationship to the procedure will be used.

### **11.5.2 BEST CORRECTED VISUAL ACUITY (BCVA)**

The number and percent of eyes reporting with BCVA of 20/20 or better, 20/25 or better, 20/32 or better, 20/40 or better, worse than 20/40 to 20/80, worse than 20/80

to 20/200, and worse than 20/200 at each visit will be summarized. The number and percent of eyes reporting BCVA of increase  $\geq 10$  letters, increase 10 letters, increase  $\geq 5$  letters to  $< 10$  letters, within 5 letters change, decrease  $\geq 5$  letters to  $< 10$  letters, decrease 10 letters, and decrease  $\geq 10$  letters at each postoperative visit will be calculated.

[REDACTED]

[REDACTED]

[REDACTED]

### **11.6 INTERIM ANALYSIS**

The primary analysis for this study will occur after the final subject reaches their 12-month follow-up. Endpoints listed below will be analyzed at an interim analysis performed when 80% of subjects reach 6 months follow up. No device effectiveness will be claimed based on the interim analysis outcomes.

Effectiveness outcomes up to 6 months will be summarized descriptively:

1. Percent of eyes with a  $\geq 20\%$  reduction in IOP with no increase in IOP-lowering medications compared to screening visit
2. Percent of eyes with IOP between 6 and 18 mmHg with no increase in IOP-lowering medications compared to screening visit
3. Percent of eyes with IOP between 6 and 21 mmHg with no increase in IOP-lowering medications compared to screening visit
4. Reduction in mean IOP from screening visit; and
5. Reduction in mean number of IOP-lowering medications from screening visit for the subjects who are on medications at the screening visit

[REDACTED]

[REDACTED]

### **11.7 DEVIATION FROM THE STATISTICAL PLAN**

Any deviations from the statistical plan will be noted in the final report.

## 12 MONITORING PROCEDURES

Sight Sciences or contract research organization (CRO) personnel will monitor the study in a manner consistent with FDA regulations, good clinical practices and the clinical research standards adopted by Sight Sciences. Study monitoring will be executed using on-site visits, via remote means, or a combination of both, and will involve the following elements:

- Site Qualification: Sight Sciences or CRO personnel will meet with investigators and clinical study staff prior to the initiation of the study in order to review the adequacy of the subject population, facilities, and equipment with respect to the needs of the study, and to familiarize the investigator with the study protocol. If Sight Sciences or the CRO have recently been involved with an investigator for another study, a site qualification visit may not be necessary.
- Site Initiation: Sight Sciences and/or CRO personnel will meet with the investigator(s) and clinical study staff when the site is ready to begin enrolling subjects in order to train them in how to properly select subjects, perform the study procedure, and record study data. This visit will include, but not be limited to a review of the following:
  - Detailed review of the protocol
  - Informed consent procedures
  - Instructions for the surgical procedure
  - Records and reports
- Interim Monitoring: Sight Sciences or CRO personnel will conduct routine visits either remotely or in-person, during the course of the study to review charts, perform source document verification, ensure proper adherence to the study protocol, and to review regulatory documents. Interim monitoring visits and telephone consultation will occur as necessary during the course of the study to ensure the proper progress and documentation of the study findings.
- Study Close Out Visit: At the conclusion of the trial there will be a study closure visit during which several actions, including but not limited to the following, will be performed:
  - A final inspection of the study binder
  - Accountability and return of all devices and non-consumable ancillary study supplies to the sponsor
  - Discussion of record retention requirements with the investigator
  - Close-out notification to the IRB

## **13 DATA AND QUALITY MANAGEMENT**

### **13.1 DATABASE MANAGEMENT**

The study database will be designed using an electric data capture (EDC) system that is compliant with 21 CFR Part 11 and relevant guidance documents. The EDC will be developed and maintained by an independent, qualified data management firm.

The database will incorporate time-stamped audit trails, protection of human subjects, restricted access, and data security at the component level. Each database module, including each individual eCRF, will be validated by conducting a series of standard tests that demonstrate usability and correctness of the database system. The database will be maintained on an ongoing basis and will be routinely backed up.

### **13.2 SUBJECT IDENTIFICATION**

The subjects will be identified by a six-digit subject number composed of a double-digit study identification number, a two-digit center identification number followed by a two to three-digit sequential subject number. A subject identification number will be assigned after informed consent is obtained. This will ensure that subject information contained in the study records is de-identified of personal information and kept confidential.

### **13.3 SUBJECT ACCOUNTABILITY**

All subjects enrolled and treated in this clinical investigation shall be monitored for the duration of the investigation. The clinical investigation shall be considered completed when all subjects that have been enrolled in the investigation have reached the final reporting period, excluding subjects who were withdrawn.

### **13.4 CONFIDENTIALITY**

All medical records associated with the clinical investigation will be made available for review by Sight Sciences personnel, its contract research organization (CRO) and governmental/regulatory agencies involved. The results of the study may be published in the future for scientific and marketing purposes, but the identity of each subject will not be revealed. All records will be stored in a secure area at the investigator's facility, the CRO, the data management firm and at Sight Sciences, Inc per each organization's own SOPs.

### **13.5 SOURCE DATA AND CASE REPORT FORMS**

Source data will be entered into a validated electronic system at each site by trained personnel in accordance with 21 CFR Part 11 requirements. Electronic entries will be

100% verified against corresponding source data at the sites and queried/corrected if needed to the extent possible. Medical site records serve as source data. In addition, data that are collected exclusively for the purpose of this study and not normally recorded in the subjects' medical records can be collected directly on the study worksheets provided by the sponsor and these study worksheets will serve as the source data.

Source data and study worksheets are to be maintained at the site in the subject records or in the medical records. All data entries must be made in accordance with ALCOA standards and GDP.

### **13.6 RETENTION PERIOD**

Clinical sites are to retain any and all clinical trial material (documentation, photographs, etc.) for a period of two years from the date a marketing application is approved or two years after the investigation has been discontinued, or as directed by their institutional document retention requirements, whichever is the longest. After that time, the items must be returned to Sight Sciences for archiving.

## **14 PROTOCOL MODIFICATIONS AND DEVIATIONS**

Protocol modifications may occur during the study. Each will be approved by the sponsor before implementation. Each will undergo Institutional Review Board (IRB) review and approval, as necessary.

Any deviations from this protocol intended to protect the life or physical well-being of a subject in an emergency are to be reported to Sight Sciences, Inc. as well as the IRB as soon as possible, and no later than 5 working days after the emergency occurred.

All protocol deviations will be documented using the Protocol Deviation form.

## **15 DEVICE FAILURES AND MALFUNCTIONS**

All device failures or malfunctions should be recorded on the Customer Experience Form and reported to Sight Sciences Customer Service [contact]).

## **16 ETHICAL CONSIDERATIONS**

### **16.1 DECLARATION OF HELSINKI**

This study shall be conducted in accordance with the Declaration of Helsinki (Appendix D).

## **16.2 INSTITUTIONAL REVIEW BOARDS (IRB)**

The study shall not begin at a site until approval has been obtained from the reviewing IRB. It is the Investigators' responsibility to obtain and maintain written approval of the study protocol and Informed Consent documents from the appropriate IRB. It is also the Investigators' responsibility to notify that body about any amendments to these documents and to follow the IRBs rules regarding the reporting of Adverse Events and Protocol Deviations related to the device and/or this study. Copies of all written approvals (identifying the study, the submitted and approved documents and the date reviewed) and the approved versions of the documents must be provided to Sight Sciences or its CRO.

The Investigators must file all correspondence with the IRB and forward copies of such correspondence to Sight Sciences.

